Among these worksites, we randomly selected 25 “treatment” worksites that would receive the wellness program and 25 “primary control” worksites for phase 2.⁵ These primary control worksites participated in data collection through PHAs and in-person biometric screenings, but did not receive the wellness program treatment. **Figure 1** shows the locations of the 25 treatment and 25 control worksites across the Eastern U.S. The remaining 110 worksites served as “secondary controls.” which were included in analyses of administrative data. Thus, the primary data described below was collected from the 50 treatment and primary control worksites; administrative data were compiled for all 160 worksites. **Figure 2** shows a Consolidated Standards of Reporting Trials (CONSORT) flow diagram for our phase 2 evaluation, including the sample sizes of treatment and control groups.

⁵ For the first 18 months of the study (phase 1), there were 20 treatment and 20 primary control sites.

Randomization at the worksite level allows us to assess the effects of interventions that aim to affect workplace culture or operate on a group level, such as using common break rooms to stage nutrition demonstrations, team-based activities, or worksite level prizes.

IV. Data

Our analysis focuses on outcomes from five data categories. The Table below displays the source of each data set and the study population from which it is derived.

Summary of the Components of Data Collected				
Data	Source	Treatment Worksites (25)	Primary Control Worksites (25)	Secondary Control Worksites (110)
Administrative Data				
Employment records	BJ's	All employees	All employees	All employees
Claims data (medical and pharmaceutical)	Cigna (via BJ's)	Employees insured by Cigna	Employees insured by Cigna	Employees insured by Cigna
Primary Data				
Biometric screening data	Wellness Workdays	Employees completing screening	Employees completing screening	None (by design)
Personal Health Assessment	Wellness Workdays	Employees completing survey	Employees completing survey	None (by design)
Participation in the treatment	Wellness Workdays	All employees	None (by design)	None (by design)

A. Administrative Data

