- *Unmanaged depression:* We defined this as responding “no” or “I have never been depressed” to the question “Depression prevention means using effective methods to keep depression from occurring, or if it does occur, to keep it as mild and brief as possible. Effective methods include controlling negative thinking every day, engaging in healthy, pleasant activities on most days, exercising for 30 minutes or more on most days, practicing stress management on most days, and getting professional help when needed. Do you effectively practice depression prevention in your daily life?”
- *Stress at work:* We defined this as answering the question “During the last 30 days, how often have you found yourself stressed or worried about problems as work?” with “sometimes,” “fairly often,” or “very often.” (rather than “almost never” or “never”).

Table 6 provides summary statistics for employees who completed the PHA in the control worksites.

B3. Program participation data

At the individual employee level, we examine three different definitions of participation based on the number of modules completed. Each module had its own set of requirements that defined completion and incentives attached to participation or completion. Details of the modules and their requirements are provided in Appendix 1.

- **Modules completed:** We defined a continuous variable denoting the number of modules completed, which ranges from 0 to 12 over the course of the study period. This serves as the primary definition of participation for this analysis.

⁷ Ware JE, Kosinski M, Dewey JE, Gandek B. How to Score and Interpret Single-Item Health Status Measures: A Manual for Users of the SF-8 Health Survey. Lincoln RI: QualityMetric Incorporated, 2001.

- **Participation indicator:** We defined a binary indicator of participation based on completing at least one module. This is a secondary definition for this analysis.⁸
- **High participation:** We defined another secondary binary indicator based on completing 3 or more modules. We chose 3 modules as the threshold for high participation based on the distribution of the number of modules completed.

Table 7 shows summary statistics on participation overall and by module across the treatment worksites for phase 1 and for phase 2 of the wellness program.

V. Study Sample

A. Main sample and subsamples

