estimates of the effect of the treatment. Therefore, we model the impact of participation on outcomes using a two-stage least squares (2SLS) specification:

$$Y_{ijt} = \gamma_0 + \gamma_1 PARTICIPATION_{ijt} + \gamma_2 X_{ijt} + \mu_{ijt} \quad (3)$$

Where the endogenous *PARTICIPATION* variable is estimated via the first stage regression:

$$PARTICIPATION_{ijt} = \pi_0 + \pi_1 TREATMENT_{jt} + \pi_2 TIME_WORKED_{ijt} + \pi_3 TREATMENT_{jt} * TIME_WORKED_{ijt} + \pi_4 X_{ijt} + v_{ijt} \quad (4)$$

We include the exposure interaction in the first stage, parallel to our ITT estimates. The coefficient γ_1 in equation (3) identifies the effect of participation on outcomes.

On the left-hand side of the first stage, this base specification uses the continuous definition of participation, with values from 0-12, which indicates the number of modules an individual participated in during the 36-month study period. **Table 10** shows the results of first stage estimates for this and for our alternative definitions of participation (including indicators for completion of 3 or more modules of the program or completion of at least 1 module of the program). In robustness specifications, we use these alternative definitions of participation.

If no one in the control group receives the treatment, we can interpret the 2SLS estimates of the LATE as a treatment on the treated (TOT). Empirically, we expected this to be essentially true by construction because the control worksites did not receive the wellness modules. However, because we assigned employees to worksites based on their initial locations of employment at the beginning of the study period, a small number of employees who moved from control worksites to treatment worksites during the intervention period did receive an opportunity to participate in the program. This explains the fact that the control group means in **Table 10** are nearly, but not exactly, zero.

C. Addressing endogeneity concerns

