The key identifying assumption is that the only mechanism through which being employed in a treatment worksite affects outcomes is through the availability of the wellness program. There are two threats to this assumption. First, to the extent that covariates were not balanced at baseline and those covariates affect the outcomes of interest, that imbalance could bias our estimates. We control for observed covariates and apply weights to balance covariates between treatment and control. Despite these adjustments, unobserved covariates might still be imbalanced.

Second, to the extent that the wellness program affected hiring or tenure of employees, their presence in the data set may be endogenously determined. We address the issue of endogenous entry by pre-specifying a subsample of those who were already employed at the time the intervention began. We defined this more restrictive “stable employment” subsample as comprising employees who had worked continuously for 13 weeks prior to the wellness program. This comes at a cost of reducing the overall sample size. Our goal in choosing the definition for this subsample was to balance the costs and benefits, as detailed in Appendix 2.

In this stably employed subsample, however, exit from the firm's workforce is still potentially endogenous. We deal with this concern in two ways. First, we will test balance on exit between treatment worksites vs. from control worksites overall and for subgroups. Indeed, tenure and time worked are among our primary outcomes. To the extent that we observe any unbalanced exit, we will perform a bounding exercise (assuming that those who exited have outcomes working against any observed effects of the intervention).

D. Subgroup analyses

We pre-specified three subgroup analyses. We selected these subgroups based on differences in key outcomes within the control group for those with different baseline characteristics, such as differences in medical spending by age or in reported exercise by sex (**Table 11**).

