randomization into treatment or control, with β_1 indicating the average worksite-level effect of being randomized into treatment. The vector of covariates X_{kt} comprises the same set of observable characteristics for individuals, aggregated to the worksite level using weighted averages (generating percentages for binary variables). The worksite-level regressions are weighted by worksite size, as measured by the total hours worked by all employees at a worksite, with standard errors adjusted for heteroscedasticity. For estimates of program effect that are significant in the individual-level analysis, we will produce parallel LATE estimates at the workplace level, analogously using treatment status as an instrument for participation.

Although the employees at each worksite could change over time, the worksites themselves were all stably represented in our data. However, at the 18-month mark, 5 worksites previously in the control group entered the treatment group. In our base specification, we will assess effects for the 20 worksites that were continuously treated throughout the 3-year period (omitting the additional 5 from the analysis altogether). As an alternative specification, we will also evaluate effects at the worksite level when considering the 5 additional worksites in the treatment group.

F. Sensitivity analyses

We conduct several types of sensitivity analyses. First, in the statistical analyses above, our base regression models use linear regression even for binary outcomes. The OLS estimator has been shown to perform better than other non-linear approaches in estimating the average population effect, particularly with large samples.¹⁰ However, OLS also has limitations, such as its sensitivity to outliers. To test the robustness of our main results to changes in functional form, we will fit logit models for binary outcome variables.

Second, we will present LATE results with alternative definitions of participation. As defined above, these include a binary indicator of participation based on completing at least one module, and a high participation indicator defined as completing at least 3 modules.

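### The secondary LATE for 3 or more modules codes completers of 1–2 modules as untreated, so it measures the effect of high participation only if 1–2 modules have no effect

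*Combined protocol and SAP*

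**What the plan says.** Section IV.B3 defines three participation measures. The count of modules completed, 0 to 12, comes first: "This serves as the primary definition of participation for this analysis". A completed-any-module indicator is secondary, and so is the high-participation indicator: "We defined another secondary binary indicator based on completing 3 or more modules". The cut-point is explained in one sentence: "We chose 3 modules as the threshold for high participation based on the distribution of the number of modules completed". No argument is given that 1 or 2 modules should have no effect.

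Section VI.B says of the two secondary measures: "In robustness specifications, we use these alternative definitions of participation". Section VI.F lists them again, including "a high participation indicator defined as completing at least 3 modules".

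On interpretation, section VI.B says that if nobody in the control group is treated, "we can interpret the 2SLS estimates of the LATE as a treatment on the treated (TOT"). It explains that control participation is close to zero apart from a few employees who moved sites. The identifying assumption in section VI.C is that "the only mechanism through which being employed in a treatment worksite affects outcomes is through the availability of the wellness program". Neither section mentions employees who take part but fall below the three-module cut-point.

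**The concern.** For an instrumental-variable estimate to be the effect of a given treatment variable, assignment must act on the outcome only through that variable. The assumption in section VI.C concerns availability of the program as a whole. That is weaker than saying assignment acts only by taking people to three or more modules. Under the 3+ indicator, people whom assignment leads to complete 1 or 2 modules count as untreated. Any effect in them enters the numerator (the ITT) but not the denominator (the first stage).

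The plan's other two definitions both give these employees a non-zero dose, so its own primary model contradicts the zero that the 3+ version assigns. Following section VI.B as written, an analyst could label the 3+ coefficient a TOT effect because controls were untreated, although that condition says nothing about partly treated employees coded 0. A larger coefficient for high participation could then be taken as support for a larger effect at higher doses.

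**Working it through.** **Inputs.** Table 7 Panel B: 7,288 treatment-site employees and 2,071 participants; 28.4% completed any module and 16.7% completed 3 or more; mean modules 1.17 per employee and 4.11 per participant. Table 10 Panels A and B: first-stage estimates for any module, modules completed and 3 or more modules. Table 10 prints one figure per cell, read here as the average effect of assignment.

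**Reproducing the plan's figures.** 2,071/7,288 = 28.4%. 16.7/28.4 = 58.8%, as printed. 1.17/0.284 = 4.12, against 4.11 printed (rounding).

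**Size of the miscoded group.** Table 7B: 28.4 − 16.7 = 11.7% of treatment-site employees, or 0.117 × 7,288 ≈ 853 people; 100 − 58.8 = 41.2% of participants. Table 10, all employees: 27.53 − 15.95 = 11.58 points.

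**Formula.** Let p3 and p12 be the shares that assignment moves into 3+ and into 1–2 modules, and E3 and E12 the average effects in those groups against no module. Take the effect on employees who complete none as zero. Then ITT = p3·E3 + p12·E12. With one instrument:

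- LATE(3+) = ITT/p3 = E3 + (p12/p3)·E12
- LATE(3+)/LATE(any) = (p3 + p12)/p3

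The second line holds whatever the outcome data show. The first equals E3 only if E12 = 0.

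**Overstatement of E3, all employees.** p12/p3 = 11.58/15.95 = 0.726.

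- E12 = 0: factor 1.00
- E12 = half of E3: 1 + 0.5 × 0.726 = 1.36
- E12 = E3: 1 + 0.726 = 1.73
- Effect linear in modules, with the 1–2 group averaging between 1 and 2 modules (an assumption, since the split is not given): 1.12/(1.12 − 0.1158 × 1) = 1.12 to 1.12/(1.12 − 0.1158 × 2) = 1.26. In module terms, the coefficient stands for 1.12/0.1595 = 7.0 modules, while the 3+ group averaged 5.6 to 6.3.

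**The same steps in the other samples (Table 10 Panels A and B).**

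| Sample | Any, points | 3+, points | p12, points | Factor if E12 = E3 | Factor if linear |
|---|---|---|---|---|---|
| All | 27.53 | 15.95 | 11.58 | 1.73 | 1.12–1.26 |
| PHA | 63.06 | 46.74 | 16.32 | 1.35 | 1.05–1.10 |
| Cigna | 57.31 | 43.29 | 14.02 | 1.32 | 1.05–1.10 |
| Stably employed | 49.75 | 35.04 | 14.71 | 1.42 | 1.06–1.13 |
| Stably employed, PHA | 79.22 | 67.78 | 11.44 | 1.17 | 1.02–1.04 |
| Stably employed, Cigna | 59.54 | 45.79 | 13.75 | 1.30 | 1.04–1.09 |

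The factor is 1.00 in every row if E12 = 0.

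**Base model.** Equation (4) has more than one instrument, because treatment is interacted with time worked, so the coefficient is not a simple ratio. An illustrative simulation with assumed inputs (not calibrated to Table 10, and with time worked kept as a second-stage control) gave these ratios of the 3+ coefficient to the true 3+ effect:

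| Effect of 1–2 modules | One instrument | With the interaction |
|---|---|---|
| None | 1.00 | 1.00 |
| Half the 3+ effect | 1.23 | 1.14 |
| Equal to the 3+ effect | 1.46 | 1.28 |
| Linear in modules | 1.18 | 1.17 |
| Opposite sign, half size | 0.77 | 0.86 |

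The direction carries over to the base model; the exact factors do not.

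**The case against.** The other side has good points, and several of them stand.

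- **The bias is not automatic.** A reader might infer that the 3+ estimate is inflated by construction. The documents do not support that. Only the ratio to the any-module LATE is mechanical, and that ratio is a change of units between two estimands. Bias against the true 3+ effect depends on the effect of 1–2 modules, and the documents give no outcomes by module count.
- **The factors belong to a single-instrument model.** They are exact for the phase 1 comparison model (equations 7–9) but not for base equation (4), and the plan does not say that the 3+ definition will be run in the phase 1 model.
- **The largest figures apply to the full employee sample**, which serves the employment outcomes of Table 3. Spending, biometric and survey outcomes use the Cigna and screened or surveyed samples, where the factors are smaller.
- **The analysis is secondary.** The primary LATE uses the module count. Tables 3–6 have one 2SLS column per sample, Table 10 prints every first stage, and nothing in the plan proposes to infer dose-response from comparing definitions. With one instrument, the test of no effect is essentially the same as for the ITT.

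A reader might also infer that group-level delivery is a reason to drop this indicator, since section III says worksite randomization "allows us to assess the effects of interventions that aim to affect workplace culture or operate on a group level". That does not follow. If employees who complete no module are affected, all three definitions are touched alike, including the two that would be kept. Section VI.A also notes that worksite-level delivery makes the ITT and worksite analyses informative.

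What none of this answers is that the stated TOT condition is insufficient for the 3+ definition, and that the plan nowhere says so.

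**Conclusion.** The point holds as a missing assumption and an unsafe label on a secondary analysis. The 3+ coefficient is the effect of completing three or more modules only if completing one or two does nothing. The plan does not argue this, and its primary 0–12 count assumes otherwise.

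If the effect of 1–2 modules lies between zero and that of 3+, the overstatement is 1.00–1.73 for all employees, 1.00–1.35 in the PHA sample and 1.00–1.32 in the Cigna sample. If effects are linear per module, it is 1.12–1.26 for all employees and about 1.05–1.10 in the PHA and Cigna samples. An opposite-sign effect would bias the estimate the other way. These figures assume one instrument and no effect on employees who complete no module, and they are approximate for the base model. The size cannot be narrowed from the documents. The ITT and the primary LATE do not depend on this coding.

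**What to change.** In sections VI.B and VI.F, do one of two things:

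1. Drop the 3+ indicator as a 2SLS treatment, keeping it as a descriptive statistic in Table 7 and a first-stage outcome in Table 10.
2. Keep the column, but report it only as the ITT rescaled by the 3+ first stage. State that reading it as the effect of 3+ modules requires 1–2 modules to have no effect. Do not present it as a TOT effect, as a robustness check on effect size, or as evidence of dose-response.

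In either case, amend the TOT sentence in section VI.B to say that, besides untreated controls, it requires no program effect on employees whom the chosen participation measure codes 0.

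The cost is a few sentences and the loss or relabelling of one secondary robustness column. No data collection or primary analysis changes.

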- **Hours and earnings:** Each employee's hours (including working hours, vacation, sick time, personal time) and earnings in each pay period. Each observation is at the employee, pay-period, earnings-type level. These data include a handful of negative payments/hours that indicate corrections.

We used these data to study several outcomes:

- **Absenteeism:** We calculated absenteeism as an employee's number of sick plus personal hours, divided by the sum of an employee's number of sick, personal, and worked hours. This gives the ratio of absence relative to how much an employee usually works. Vacation and holiday time are excluded from both the numerator and denominator.
- **Performance review:** Employee performance reviews were coded on a 5-point scale, with 1 representing the best performance rating and 5 the worst. We averaged performance review scores (weighted by the duration of time over which a score held) and created a binary indicator where a score of less than 3 was coded as good performance and 3 and greater as poor performance.
- **Employment tenure:** We calculated each worker's length of tenure at BJ's and how many hours he or she worked (including the nature of those hours, such as regular hours and overtime). We defined tenure as the difference between the hire date and the latest

termination date. If there was no hire date recorded in the data, we used the first appearance in our database. If there was no termination or retirement date in the data, we used the end of the study period.

Table 2 provides a summary of demographic and employment characteristics of the population. The data are presented at the employee level (overall and for analytical subsets) and at the worksite level. **Table 3** provides summary statistics for tenure, performance review, and absenteeism gathered among the control worksites during the treatment period.

A2. Medical and pharmaceutical claims data

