In this representative estimating equation, Y_{ijt} denotes an outcome of interest, such as medical spending, for individual i who is employed in worksite j at time t . $TREATMENT_{jt}$ is a binary indicator of whether the individual's worksite was randomized into treatment or control. We assigned each individual to the worksite at which he or she was employed when the treatment began in January 2015. $TIME_WORKED_{ijt}$ is the share of total available work hours in the study period that the individual actually worked; it is expressed in percentage terms. The effect of randomization to a treatment worksite is allowed to vary based on exposure to the treatment (measured via time worked during the treatment period). The treatment effect is captured by $\beta_1 + \beta_3 * Exposure$. The average effect of randomization into the treatment group can be summarized by assessing this at the average level of exposure. While we will produce estimates of the average effect of randomization into treatment, as captured in the layout of Tables 3-6, we will additionally show results for both β_1 and β_3 for each of our results in a set of parallel tables.

X_{ijt} represents a vector of covariates that may help improve precision as well as account for chance differences in characteristics between treatment and control groups, including:

- Age indicators: <20 years (omitted), 20-29, 30-39, 40-49, 50-59, and 60 and greater.
- Sex indicator: male (omitted), female
- Age-sex interactions
- Race: white (omitted), black, Hispanic, and other
- Employment characteristics (measured at baseline for the stably employed subsample):
 - Part-time (omitted), full-time
 - Salaried (omitted), hourly
 - Sales worker (omitted), non-sales worker, and other worker.

ε_{ijt} is the idiosyncratic error term. The models are weighted using the sample weights described above. Standard errors were clustered at the worksite level.

B. Local average treatment effect (LATE)

While our ITT analysis explores the effect of being randomized into a treatment worksite, a related but distinct question is: what is the effect of participating in the wellness program on the outcomes of interest? The answer to this second question will be different if not all employees in treatment worksites elect to participate. Because the choice to participate in the program is endogenous, simply including participation as a right-hand side variable may produce biased

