Notes: Table reports the coefficient on TREATMENT from estimating equation (1) by OLS (column 2), and the coefficient on PARTICIPATION from estimating equation (2) by IV (column 3). Standard errors are listed in parentheses. Column 1 reports the mean of each employment outcome in the control group for each sample (with standard deviation in parentheses, followed by the number of observations for each outcome). All regressions will include demographic and employment controls (age, sex, age-sex interactions, race/ethnicity, Cigna coverage status, full-time status, paid hourly status, and job category) and cluster standard errors at the worksite (for employee-level regressions). Employee-level and stably employed subsample control means are weighted by a weight that balances treatment and control on demographic characteristics. Worksite-level control means are not traditionally weighted: individual-level records are collapsed at the worksite-level and weighted by the total number of hours worked at each worksite. For worksite level results on tenure, the outcome was defined as the percent of total days at the worksite during the study period that was worked by employees at the worksite.

§ Tenure was defined as the number of days worked during the treatment period for the employee-level mean and stably employed subsample mean; it was defined as the percent of the entire treatment period worked by employees in the worksite-level mean.

Table 4: Impact on Medical & Pharmaceutical Spending and Utilization

	Employee-level			Stably Employed Subsample			Worksite-level (per 2000 work hours)		
	Mean in Control Group (1)	Reduced Form (Linear) (2)	2SLS (Linear) (3)	Mean in Control Group (1)	Reduced Form (Linear) (2)	2SLS (Linear) (3)	Mean in Control Group (1)	Reduced Form (Linear) (2)	2SLS (Linear) (3)
Medical Spending									
Total Spending	4800.57 (18559.82)			4721.85 (19056.92)			5044.74 (2994.54)		
Medical Utilization									
Number of Office visits	3.90 (4.47)			3.95 (4.33)			4.21 (0.93)		
Number of Hospitalizations	0.09 (0.40)			0.08 (0.36)			0.08 (0.05)		
Number of ER Visits	0.28 (0.75)			0.26 (0.61)			0.27 (0.11)		
Pharmaceutical Spending									
Total Spending	1237.60 (6921.32)			1227.32 (7115.67)			1317.72 (1145.17)		
Pharmaceutical Utilization									
Number of Distinct Medications	5.49 (6.44)			5.91 (6.54)			6.00 (1.30)		
Total Medication Months	11.20 (19.31)			11.41 (19.37)			12.39 (4.38)		
N	7,174			5,779			135		

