Similarly, Figure 1B shows a similar analysis when we extend the definition of retention to 12/1/2015. This graph contains only control worksite employees, because tenure itself may be affected by the wellness program and is an outcome we will examine formally in the analysis. To extend the above example of interpretation, of the 10,000 employees in control worksites who were employed through the first 17 weeks of 2014, about 64% were still employed on 12/1/2015. This decrease is from 79% at the beginning of 2015, implying that 15% of the sample (79% – 64% = 15%) were “lost” from the sample (e.g. terminated, left BJ’s) during the first 11 months of 2015.

Analyzing samples defined with respect to 3/1/2015 (start of the first module): Figure 2 takes a different approach to looking at tenure. It looks at retention for samples of employees defined based on the number of continuous weeks worked immediately *before* the wellness treatment

launched (i.e. defined by counting backwards from 3/1/2015). Retention here is still defined as appearing in 12/1/2015. As above the figure contains only employees from control worksites.

As an example of interpretation, there were about 13,500 employees in control worksites who worked during the 13 continuous weeks (~3 months) before the start of the wellness program (counting back from 3/1/2015 -- i.e. Feb '15, Jan '15, and Dec '14). Among these 13,500 employees, about 10,000 remained actively working on 12/1/2015. This amounts to about a 75% retention rate.

We examined the rate of decline of this sample of employees among control worksites throughout the treatment. Figure 3 shows the rate of decline of the above control sample (those who worked for the 13 consecutive weeks leading up to the start of the treatment (3/1/2015), and illustrates the decline in the number and percent of this sample through 2017. The X axis shows the months elapsed since start of the treatment (0 is the end of February 2015, while 34 is the end of December 2017). This graph shows a smooth decline in the sample of employees to reach 51% by the end of December 2017

Figure 3. Tenure Analysis (Control TMs)

Sample: C TMs employed during the 13 weeks before the intervention

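### For tenure, a named primary outcome, the base employee-level model adjusts for hours worked after randomisation, so it does not estimate the intention-to-treat effect

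*Combined protocol and SAP*

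**What the plan says.** - **Model.** Equation (1) in Section VI.A contains TREATMENT, TIME_WORKED, their product and covariates. TIME_WORKED "is the share of total available work hours in the study period that the individual actually worked". The average effect is β₁ + β₃ × average exposure.
- **Status of tenure.** Section VI.C: "Indeed, tenure and time worked are among our primary outcomes". Appendix 2 adds that "tenure itself may be affected by the wellness program and is an outcome we will examine formally in the analysis".
- **Model used for tenure.** The notes to Table 3, which has a tenure row, read "Table reports the coefficient on TREATMENT from estimating equation (1) by OLS (column 2". Nothing exempts tenure. The table's footnote says: "Tenure was defined as the number of days worked during the treatment period for the employee-level mean and stably employed subsample mean".
- **A second definition.** Section IV.A1 has a longer span: "We defined tenure as the difference between the hire date and the latest" termination date.
- **What column 2 holds.** Section VI.A says "we will produce estimates of the average effect of randomization into treatment, as captured in the layout of Tables 3-6", with β₁ and β₃ also shown in parallel tables. The table notes instead make column 2 the TREATMENT coefficient, and for column 3 they cite an equation (2) that the plan does not contain.
- **Related checks.** Section VI.C: "we will test balance on exit between treatment worksites vs. from control worksites overall and for subgroups", with bounding if exit is unbalanced. Section VI.F plans a treatment-dummy model, equation (7), for comparison with phase 1. Section VI.E has a worksite model, equation (6).

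**The concern.** Someone who stays longer works more of the period's hours. Holding TIME_WORKED fixed therefore compares the tenure of treated and control workers who worked similar hours, and that comparison takes out much of what the program could have changed. The plan itself accepts that tenure may respond to treatment.

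A reader of Table 3 would take the tenure row as the ITT answer on a primary outcome. If the program does improve or worsen retention, that row would show only part of the effect.

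**Working it through.** The plan gives no power or effect-size figure for tenure. What can be reproduced is the control tenure distribution in Table 3.

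**Inputs from the documents**
- Period P: January 2015 to December 2017, 365 + 366 + 365 = 1,096 days.
- Control tenure, stably employed: mean 786.57 days, SD 376.96 (Table 3).
- Job classes in that group: 11.6% full-time salaried, 38.6% full-time hourly, 49.8% part-time (Table 2).
- Standard weekly hours: 40, 35.8 and 20 (Table 8, Panel D, all controls).

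**Assumptions**
- Exit is exponential, and the effect is a 10% longer time to exit.
- The CV of weekly hours within a job class is 0 to 0.6 (lognormal).
- The denominator of TIME_WORKED is the same for every worker.

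**1. Identity.** With balanced covariates, ITT − (β₁ + β₃m) = β₂(m₁ − m₀) + β₃(m₁ − m). Here m₁ and m₀ are the arm means of TIME_WORKED, and m is the mean at which the effect is evaluated. The gap vanishes if the arms work equal hours (m being that common mean) or if β₂ and β₃ are both zero. For tenure, β₂ cannot be near zero.

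**2. Fit to the controls.** θ(1 − exp(−P/θ)) = 786.57 gives θ = 1,555 days. The simulated SD is 378. The share still employed at period end is exp(−1,096/1,555) = 49%; Appendix 2 gives 51%.

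**3. True effect.** 1.1θ(1 − exp(−P/1.1θ)) − 786.57 = 809.28 − 786.57 = 22.7 days.

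**4. Equation (1).** It was fitted with full-time and salaried status as covariates. Each simulated worker appears under both arms, so there is no chance imbalance. Percentages are shares of the true effect.

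| CV of hours | β₁ + β₃m, days | Recovered | β₁ alone | Effect in full-timers only | Effect in part-timers only |
|---|---|---|---|---|---|
| 0 | 1.9 | 8% | 33% | −19% | 36% |
| 0.2 | 5.6 | 25% | 70% | 2% | 47% |
| 0.4 | 11.7 | 51% | 110% | 37% | 65% |
| 0.6 | 15.7 | 69% | 122% | 60% | 78% |

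Columns 2 to 4 are for an effect spread over all workers; the last two use β₁ + β₃m. Check at CV 0.4: 7.630 × 1.472 − 0.2584 × 0.736 = 11.23 − 0.19 = 11.0 days lost, and 22.7 − 11.0 = 11.7. With no true effect the estimate is zero.

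**5. Denominator.** If available hours means each worker's own standard hours over the period, recovery is 0% at CV 0 and 17–67% at CV 0.2–0.6. If it meant hours available while employed, recovery would be 100%, but the definition refers to the study period.

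**6. With clustering.** Set-up: 160 sites, 25 treated, 96 stable workers each, true gain about 51 days. The treatment-dummy model gave 47–55 days (SE 9–12). Equation (1) gave 12–14 days (SE 4–5) at CV 0.2 and 28–31 days (SE 7–8) at CV 0.4. The SE shrinks along with the estimate, so the fault is a wrong estimate more than lost significance.

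**7. Whether a planned analysis already covers this**
- Equation (7) drops TIME_WORKED, but it is a sensitivity analysis with the phase 1 weights, and Section VI.F says phase 1 weighted people by exposure.
- Equation (6) aggregates with hours-worked weights. Table 3 puts worksite tenure at 76.08% of the period, against 416.69/1,096 = 38.0% per employee. Weighting tenure by its own length gives 416.69 + 399.87²/416.69 = 800 days, or 73%, so the worksite figure looks like a different quantity.
- The exit-balance test has no stated model and does not fill the tenure row.

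**The case against.** The strongest objection concerns the all-employee sample. Anyone employed at any time is included, and Sections V.A and VI.C warn that entry may respond to treatment. Better retention means fewer hires, so even a treatment-dummy model does not give a clean ITT effect there. Table 3 implies 41,376 × 416.69/1,096/135 = 116.5 workers per control site at a time, close to the 118 in Section III. Assume constant headcount, each leaver replaced, and hire spells averaging 247 days. A 10% longer stay then adds 13.7–16.0 days for a fixed set of workers, but the dummy model returns 25.5–29.7, and the number ever employed falls 6–7%. This stands: no all-employee percentage is claimed, and the fix centres on the stably employed.

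Other objections also stand in part:
- The exit-balance test could reveal a retention effect, so the plan is not blind to one. It still does not supply the tenure estimate.
- Because β₁ and β₃ will appear in parallel tables, the conflict over column 2 is a labelling error and minor.
- A reader might infer that the program's effect on time worked is certain to be reported as nil. Time worked has no row in Table 3, and no section applies equation (1) to it; only if that were done would the effect be zero by construction.
- A reader might infer a wrong-signed tenure result. In these runs that occurs only for an effect confined to full-timers with almost no spread in hours: −19% at CV 0, already +2% at CV 0.2.

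**Conclusion.** The point holds for tenure and should be settled before the arms are compared; the plan's introduction says post-treatment outcomes had not been compared by arm over this window. Equation (1) at average exposure is not the ITT effect on tenure. It shrinks a real retention effect and does not create one where none exists.

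In the stably employed subsample it recovers about 8% to 69% of a spread effect over assumed CVs of 0 to 0.6. That range rests on the CV, the exponential exit and a common denominator. The attenuation needs only that TIME_WORKED rises with tenure and that the effect is spread over workers.

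A reader might extend this to every outcome in Tables 3–6. The documents do not support that: the gap depends on how far hours worked differ between arms, and its size and direction are unknown.

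**What to change.** 1. **Tenure, and time worked if reported.** Make the primary employee-level ITT a treatment-dummy model (the form of equation (7)) in the stably employed subsample. Use the base balance weights, covariates fixed before treatment and worksite-clustered SEs. Leave out TIME_WORKED, any exposure or hours weights, and Cigna coverage measured during the treatment period. The Table 3 notes list Cigna coverage as a control, and the Table 10 notes describe it as coverage at any time in that period. Report the same model for all employees, labelled as open to endogenous entry. Keep equation (1) for tenure only as a labelled dose-response analysis.
2. **Minor, other outcomes.** Show the treatment-dummy model without exposure weights beside equation (1).
3. **Minor, notes to Tables 3–6.** State that column 2 is the effect at average exposure, and replace the citation of equation (2) with equation (3).
4. **Minor, definitions.** Reconcile the tenure definitions in Section IV.A1 and the Table 3 footnote, and define total available work hours.

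The cost is wording and a small amount of extra analysis, since the model form is already planned; its weights must be restated. The SE for tenure will be larger than equation (1) would show.
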